#### **10.4 Events of Special Interest**

Not applicable.

#### **10.5 Other Safety Considerations**

##### **10.5.1 Laboratory Data**

All laboratory data obtained during the study should be reviewed. Any abnormal value that leads to a change in subject management (eg, requirement for additional medication or monitoring) or is determined to be of clinical significance by the Investigator should be reported as an AE and/or SAE as appropriate, unless this value is consistent with values obtained before entry into the study.

### 10.5.2 Medication Errors

Any medication error that results in an AE, even if it does not meet the definition of serious, requires reporting within 24 hours to the safety Medical Monitor. Refer to [Section 10.2.3.2](#) for more information.

### 10.5.3 Overdose

For the purposes of this study, an overdose of SYNT001 is defined as a dose that is two-fold higher than the intended dose for the subject. As all dosing for this study will be conducted in a controlled clinical setting, an overdose is not anticipated. In the unlikely event an overdose should occur, it should be reported as an AE.

### 10.5.4 Pregnancy

If a female subject or the female partner of a male subject becomes pregnant during the course of the study, the Investigator must report the pregnancy to Medpace Safety using the **Pregnancy Reporting Form** within **24 hours** of becoming aware of the event. The Investigator must obtain consent to collect pregnancy information (including the status of the newborn, if applicable).

If some of the information required for completion of the Pregnancy Reporting Form is unavailable at the time of the initial report, follow-up reports will be completed and submitted within 24 hours of becoming aware of the new information. Any pregnancy will be followed through delivery for the observation of any SAEs. Any SAE that occurs during pregnancy must be recorded on the SAE report form in the EDC system (eg, maternal serious complications, therapeutic or spontaneous abortion, ectopic pregnancy, stillbirth, neonatal death, congenital abnormality, birth defect) and reported within 24 hours in accordance with the procedure for reporting SAEs (see Section 10.2.3.2).

## **11. STATISTICAL CONSIDERATIONS**

### **11.1 General Design**

This study is being conducted to evaluate the safety, tolerability, PK, PD, activity, and immunogenicity of SYNT001 in pemphigus patients.

### **11.2 Study Populations**

Three populations will be employed in the analysis of study data:

- The **Safety** population will consist of all subjects who have received at least one dose of study drug.
- The **PD** population will consist of all subjects who receive at least one dose of study drug and have post-dose PD data available.
- The **PK** population will consist of all subjects who receive at least one dose of study drug and have post-dose PK data available.

Primary safety analyses will be performed on the safety population. Demographics, subject disposition, screening, and baseline characteristics will be summarized for the safety and PD/PK populations, where appropriate.

### **11.3 Sample Size Justification**

Formal sample size calculations were not performed. The number of subjects was chosen based on feasibility and was considered sufficient to meet the study objectives.

### **11.4 Statistical Analysis**

#### **11.4.1 Statistical Analysis Plan**

Detailed methodology for summary and statistical analyses of the data collected in this study will be documented in a statistical analysis plan (SAP). The SAP may modify the plans outlined in the protocol; however, any deviations from the previously approved statistical plan will be described and justified in a SAP amendment. Additional statistical analyses other than those described in this section may be performed if deemed appropriate and will be described in the SAP. The SAP including pharmacokinetic data analysis methodologies will be finalized prior to database lock.

All descriptive and inferential statistical analyses will be performed using Statistical Analysis System (SAS) version 9.4 or later. Missing data will not be imputed unless otherwise stated. All clinical data captured will be provided in data listings.

Methods of handling of missing data for different endpoints will be further specified in the SAP. In general, where individual data points are missing because of insufficient samples, dropouts, or other reasons, the data will be analyzed based on reduced denominators unless specified otherwise in the SAP.

## 11.4.2 Statistical Methodology

All clinical data captured will be provided in data listings. Subject disposition, demographic information, and baseline characteristics will be presented. Baseline will be defined at the last value obtained prior to the first dose of study drug. Results will be summarized by dose level and cohort. Any discrepancy between treatment to be given and treatment received will be accounted for in these displays.

Continuous data will be summarized using descriptive statistics: number of subjects (N), number of observations (n), mean, median, standard deviation (SD), minimum, and maximum.

Categorical data will be summarized using frequencies and percentages. When categorical data will be presented, the percent will be suppressed when the count is zero to draw attention to the non-zero counts. The denominator for all percentages, unless otherwise specified, will be the number of subjects in the specified analysis population.

## 11.4.3 Analysis of Primary Endpoints

### 11.4.3.1 Safety Data

All statistical analysis of safety outcomes will be descriptive. Safety observations and measurements include AEs, treatment-emergent AEs (TEAEs), SAEs, clinical safety laboratory tests, vital sign measurements, physical examinations, and ECGs. The incidence of AEs, TEAEs and SAEs will be summarized by cohort, severity and relationship to study product.

TEAEs will be summarized using the Medical Dictionary for Regulatory Activities (MedDRA®; Version 19 or higher) System Organ Class (SOC) and preferred term, classified from verbatim terms. The incidence and percentage of subjects with at least one occurrence of a preferred term will be included, using the most severe grade. The number of events per preferred term will also be summarized. Causality (relationship to study treatment) will be summarized separately.

TEAEs, SAEs, and AEs leading to withdrawal, dose modification, or treatment discontinuation will be listed by subject, dose, and overall per SOC and preferred terms. Duration of AEs will be determined and included in listings, along with action taken and outcome.

Laboratory results will be summarized by cohort and time point. The incidence of laboratory abnormalities will be summarized. The worst on-study grade after the first dose of study drug will be summarized. Results for variables that are not coded will be presented in the listings as below, within, and above the normal limits of the local laboratory.

Vital sign measurements and change from baseline will be summarized at each scheduled time point by cohort using descriptive statistics.

Arithmetic mean of parameters from triplicate ECG will be calculated first for each subject at each planned time point. Then summary statistics of ECG test parameters (mean of triplicate) and change from baseline to each post-dose time point will be calculated. Shift tables for ECG test result category change (normal, abnormal, clinically abnormal) from pre-dose to each post-dose time point showing number and percentage of subjects with movement between categories

will be presented by treatment group. Frequency and percentage of subjects experiencing potential QTc prolongation ( $QTcF > 450$ ) will be summarized at each time point by cohort.

Concomitant medications will be coded using WHO Drug Dictionary (WHO-DD March 2013, Type B2 or later) and the data will be summarized and presented in tables and listings.

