
Study methodology
	
Study participation requires that the subject will have completed the following periods of assessment to be performed on a weekly basis: Screening, Treatment (Baseline [Day 0], Major and Minor Dosing Visit days), and a Follow-Up (Major and Minor Visit days).
 
Throughout the study, during each period of assessment to evaluate safety and tolerability, subjects will undergo physical examinations (including weight), vital sign measurements (including pulse oximetry), clinical (safety) laboratory tests, AEs, concomitant medication assessments, and ECGs.
 
Screening Period (up to 14 days)
 
After the subject has provided written informed consent, the Investigator or other qualified study personnel will determine if the subject is eligible for the study. This will be accomplished by reviewing the inclusion and exclusion criteria, and the subject’s demographic profile, screening PDAI total activity score, and medical history.
 
Treatment Period (28 or 91 days)

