	
The treatment period includes the Baseline (Day 0) Dosing Visit day, and Major and Minor Dosing Visit days. Refer to Table 2, Table 3, Table 4, and Section 7.
 
Baseline (Day 0) Visit Day
 
In addition to the safety and tolerability assessments described above, the subject will be administered the study drug and the following procedures will be conducted: pregnancy test (if applicable), PDAI, PK, PD, and immunogenicity sample collection, photography of lesions, and serum tetanus and varicella zoster virus (VZV) antibody tests. An optional skin biopsy may be collected. HR-QoL is assessed in all cohorts except Cohort 1. A complete list of assessments is provided in Table 2, Table 3, Table 4, and Section 7.
 
Major Dosing Visit Days
 
In addition to the safety and tolerability assessments described above, the subject will be administered the study drug, and the following procedures will be conducted: PDAI, PD, and immunogenicity sample collection. A complete list of assessments is provided in Table 2, Table 3, Table 4, and Section 7.
 
Minor Dosing Visit Days
 
In addition to the safety and tolerability assessments described above, the subject will be administered the study drug, and the following procedures will be conducted: PDAI and PD sample collection. A complete list of assessments is provided in Table 2, Table 3, Table 4, and Section 7.
 
Follow-up Period/End of Study (84 days)
 
The follow-up period includes the Major and Minor Follow-up Visit days. Subjects are encouraged to participate in all visits up to and including Day 112 (Cohorts 1 and 2) or Day 175 (Cohort 3) to ensure study completion. Refer to Table 2, Table 3, Table 4, and Section 7.
 
Major Follow-up Visit Days
 
In addition to the safety and tolerability assessments described above, the following procedures will be conducted: PDAI, PD sample collection, photography of lesions and HR-QoL assessments. A complete list of assessments is provided in Table 2, Table 3, Table 4, and Section 7.
 
Minor Follow-up Visit Days
 
In addition to the safety and tolerability assessments described above, the following procedures will be conducted: PDAI and PD sample collection. A complete list of assessments is provided in Table 2, Table 3, Table 4, and Section 7.
 
Dosing for any individual subject will be discontinued (ie, further treatment with the study drug will not be given) if the subject experiences any study drug-related SAE or any study drug-related non-serious adverse event that, in the judgement of the Investigator (following consultation with the Medical Monitor, if desired) suggests that it could be unsafe to administer further study drug to that subject. Additionally, a subject will be discontinued from further treatment with study drug at the discretion of the Investigator, with consultation with the Medical Monitor if desired, if they require a significant increase in anti-pemphigus medications for the management of pemphigus.

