Study drug, dosage, and administration	
Study drug: SYNT001
 
Dosage:
 
Cohort 1: 10 mg/kg, 5 weekly IV doses
 
Cohort 2: ≤30 mg/kg, 5 weekly IV doses
 
Cohort 3: ≤30 mg/kg, 14 weekly IV doses
 
Cohort 4 (optional cohort): ≤45 mg/kg, ≤14 weekly IV doses
 
Product presentation and preparation:
 
SYNT001 provided as a liquid at a nominal concentration of 50 mg/mL. SYNT001 is diluted in dextrose 5% in water (D5W) to prepare the solution for infusion.
 
Route of administration: IV in 250 mL over 1 hour ± 15 minutes

Control, dose, and route of administration	Not applicable																										
Duration of subject participation	
The duration of subject participation for each cohort is as follows:
 
  
 Cohorta	Screening	Treatment	Follow-up	Maximum Total	
 
 Days	Weeks	
   
 1	≤14 days	28 days	84 days	126 days	18 weeks	
 
 2	≤14 days	28 days	84 days	126 days	18 weeks	
 
 3	≤14 days	91 days	84 days	189 days	27 weeks	
  
 
a. Planned dose and duration of subject participation for Cohort 4 (optional cohort) will be determined following DEC data review. All available data will be considered.
	Cohort a	Screening	Treatment	Follow-up	Maximum Total		Days	Weeks	1	≤14 days	28 days	84 days	126 days	18 weeks	2	≤14 days	28 days	84 days	126 days	18 weeks	3	≤14 days	91 days	84 days	189 days	27 weeks
Cohort a	Screening					Treatment	Follow-up	Maximum Total																			
		Days	Weeks																								
1	≤14 days	28 days	84 days	126 days	18 weeks																						
2	≤14 days	28 days	84 days	126 days	18 weeks																						
3	≤14 days	91 days	84 days	189 days	27 weeks																						

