**Table 4. Study Assessments for Cohort 3**

	Screening	Treatment Period														Follow-Up				
Visit number	1	2	3	4	5	6	7	8	9	10	11	12	13	14	15	16	17	18	19	20
Time point (study day)	-14 to -1	0	7 (±1 d)	14 (±1 d)	21 (±1 d)	28 (±1 d)	35 (±1 d)	42 (±1 d)	49 (±1 d)	56 (±1 d)	63 (±1 d)	70 (±1 d)	77 (±1 d)	84 (±1 d)	91 (±1 d)	98 (±1 d)	105 (±1 d)	119 (±3 d)	147 (±5 d)	175 or ET (±5 d)
Informed consent	X																			
Demographics/medical history	X																			
Inclusion/exclusion	X																			
Physical examination a	X	X	X	X	X	X	X	X	X	X	X	X	X	X	X	X	X	X	X	X
Vital signs b	X	X	X	X	X	X	X	X	X	X	X	X	X	X	X	X	X	X	X	X
Pulse oximetry c		X	X	X	X	X	X	X	X	X	X	X	X	X	X					
Clinical safety labs d	X	X	X	X	X	X	X	X	X	X	X	X	X	X	X	X	X	X	X	X
Pregnancy test e	X	X						X							X			X		X
Hepatitis and HIV screen	X																			
12-lead ECG f	X	X						X							X			X		
Tetanus and VZV antibodies g		X																X		X
PDAI h	X	X	X	X	X	X	X	X	X	X	X	X	X	X	X	X	X	X	X	X
PK sampling i		X													X					
Immunogenicity j		X						X							X			X		X
Study drug administration k		X	X	X	X	X	X	X	X	X	X	X	X	X	X					
Immunoglobulins l	X	X	X	X	X	X	X	X	X	X	X	X	X	X	X	X	X	X	X	X q
CIC		X	X	X	X	X	X	X	X	X	X	X	X	X	X	X	X	X	X	X
Anti-Dsg (1 and 3) antibody titers	X	X	X	X	X	X	X	X	X	X	X	X	X	X	X	X	X	X	X	X
C3 and AECA m		X														X		X		
FCGR2A by buccal swab n		X																		
RNAseq		X														X		X		
Urine IgG		X														X		X		
Immunophenotyping o		X														X		X		
Exploratory pemphigus immune response biomarkers		X	X	X	X	X	X	X	X	X	X	X	X	X	X	X	X	X	X	X
Photography p		X						X								X		X		X
HR-QoL assessments		X														X		X		X
Adverse events	To be collected from the date that the ICF is signed through the last study visit																			
Concomitant medications	To be collected from within 14 days prior to Day 0 through the last study visit																			

Abbreviations: CIC = circulating immune complexes; d = days; ECG = electrocardiogram; ET = early termination; HIV = human immunodeficiency virus; ICF = informed consent form; PDAI = Pemphigus Disease Area Index; PK = pharmacokinetic; VZV = varicella zoster virus.

- Complete **physical examination**, including weight, to be performed. Height and BMI will be additional assessments conducted at screening.

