### **3. STUDY OBJECTIVES AND ENDPOINTS**

#### **3.1 Primary Objective**

The primary objectives of this study are as follows:

- Safety: To evaluate the safety of once-weekly IV infusions of SYNT001 at different dose levels and dosing durations in subjects with pemphigus (vulgaris or foliaceus)
- Dose Selection: To determine a Minimum Effective Dose (MED) of SYNT001 as assessed by (i) total IgG level nadir and (ii) the proportion of subjects that meet the criteria for response by Pemphigus Disease Area Index total activity score (PDAI)

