## 8. STUDY ASSESSMENTS

Study assessments are performed on a weekly basis and will be comprised of the following periods: Screening, Treatment (including Baseline [Day 0]), and Follow-Up (including End-Of Study). For those subjects that complete all periods in Cohorts 1 and 2, study duration is 112 days. For those subjects that complete all periods in Cohort 3, study duration is 175 days.

Further detail on specific study assessments is provided in [Section 7](#).

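### Adverse-event percentages by cohort cover 112 days in Cohorts 1-2 and 175 days in Cohort 3, so they cannot by themselves show whether longer dosing changes the event rate

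*Protocol*

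**What the plan says.** The first primary objective (protocol section 3.1) is to evaluate safety "at different dose levels and dosing durations in subjects with pemphigus". Section 11.4.3.1 gives the summary: "The incidence of AEs, TEAEs and SAEs will be summarized by cohort, severity and relationship to study product". For treatment-emergent events the same section reports, for each preferred term, how many subjects and what percentage had it at least once, and also the number of events. Section 11.4.2 makes the head count of the analysis population the denominator of percentages unless something else is specified. All safety analysis is descriptive.

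Observation time differs by design. Section 8 states: "For those subjects that complete all periods in Cohorts 1 and 2, study duration is 112 days", and "For those subjects that complete all periods in Cohort 3, study duration is 175 days". The schedule for Cohort 3 (Table 4) has adverse events "To be collected from the date that the ICF is signed through the last study visit", and the schedules for Cohorts 1 and 2 use the same window. For Cohort 4 the synopsis says: "Planned dose and duration of subject participation for Cohort 4 (optional cohort) will be determined following DEC data review".

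The protocol text contains no rate per subject-time and no common time window for adverse events.

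**The concern.** The chance that a subject has ever had an event cannot fall as the subject is watched for longer. Event counts grow with time too, so printing them beside the percentages does not help. When columns covering 112 and 175 days stand side by side, a higher figure for Cohort 3 has two explanations: a higher event rate on longer dosing, or the same rate over more days. The planned displays do not distinguish them.

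This bears on a primary objective that names dosing duration. Cohorts 2 and 3 share the same dose ceiling (30 mg/kg) and differ by plan in the number of doses, 5 against 14. They are therefore the natural pair for judging duration, and they are also the pair with unequal observation.

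**Working it through.** **Reproducing the plan's durations.** The synopsis gives the two components as "Treatment Period (28 or 91 days") and "Follow-up Period/End of Study (84 days").

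- Cohorts 1 and 2: 28 + 84 = 112 days.
- Cohort 3: 91 + 84 = 175 days.
- Ratio: 175 / 112 = 1.5625. With up to 14 days of screening added, it is 189 / 126 = 1.50.
- Difference: 175 − 112 = 63 days. This equals 91 − 28, so every extra day is a treatment day.

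Both totals match section 8.

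**Expected crude percentage at an identical rate.** The protocol gives no adverse-event rate for this population. Assume a constant hazard, the same in all cohorts, and let p be the 112-day risk. Then the 175-day risk is 1 − (1 − p)^(175/112).

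| 112-day risk | 175-day risk | Difference (points) | Ratio |
|---|---|---|---|
| 5% | 7.7% | 2.7 | 1.54 |
| 10% | 15.2% | 5.2 | 1.52 |
| 20% | 29.4% | 9.4 | 1.47 |
| 30% | 42.7% | 12.7 | 1.42 |
| 50% | 66.1% | 16.1 | 1.32 |
| 70% | 84.8% | 14.8 | 1.21 |
| 90% | 97.3% | 7.3 | 1.08 |

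For p = 30%: 1 − 0.70^1.5625 = 0.427. On a subject-time scale the two cohorts agree by construction: −ln(0.70) / 112 × 36,525 = 116 first events per 100 person-years in each.

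**Sensitivity to the constant hazard.** If risk depended only on the number of infusions (14 / 5 = 2.8), 30% would become 1 − 0.70^2.8 = 63.2%. If all events arose at one rate in the post-treatment period, which is 84 days in each of Cohorts 1 to 3, the percentages would be equal. The size of the gap therefore depends on when events occur. This is a reason to show the periods separately.

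**What chance does at these cohort sizes.** Cohorts 2 and 3 have 4 subjects each, or up to 8 after committee review, so one subject is 25 or 12.5 percentage points. Exact sums over two binomials with the risks above give:

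| n per cohort | 112-day risk | Cohort 3 higher | Tie | Cohort 3 lower |
|---|---|---|---|---|
| 4 | 10% | 0.35 | 0.45 | 0.20 |
| 4 | 30% | 0.51 | 0.27 | 0.23 |
| 4 | 50% | 0.55 | 0.25 | 0.20 |
| 8 | 10% | 0.47 | 0.30 | 0.23 |
| 8 | 30% | 0.61 | 0.18 | 0.21 |
| 8 | 50% | 0.66 | 0.16 | 0.18 |

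Cohort 3 would show an equal or lower percentage in roughly 34% to 65% of trials.

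**Which remedy is like for like.** Treatment days are 28 / 112 = 25% of observation in Cohorts 1 and 2, and 91 / 175 = 52% in Cohort 3. A single pooled rate would mix on-treatment and off-treatment time in different proportions. A cut at Day 112 ends 112 − 91 = 21 days after the last Cohort 3 dose and discards 84 − 21 = 63 of that cohort's 84 post-treatment days, while Cohorts 1 and 2 keep all 84. Splitting by period avoids both problems.

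**The case against.** Four objections have weight.

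- **No comparison is planned.** A reader might infer that the protocol sets up a biased contrast between cohorts. The text does not support that: safety is summarised descriptively, with no test, contrast or ranking rule. This stands.
- **The extra time is treatment.** All 63 additional days are dosing days, followed by the same 84-day tail. For an objective about dosing duration, the percentage affected over the whole regimen is a proper quantity, and a longer regimen carrying more cumulative risk is part of the answer. This stands, and is why the crude table should stay.
- **No stated decision uses the percentage.** A reader might infer that the crude table would lead to the wrong dosing duration. Sections 3.4 and 11.4.3.2 define dose and duration selection on the IgG nadir and the PDAI response. Section 9.5 stops on subject counts and committee review, and the scheduled reviews are anchored at Day 42. No route from this table to the selection is shown.
- **The SAP may cover it.** Section 11.4.1 lets the SAP modify or add analyses, and the denominator rule allows exceptions. The absence of subject-time rates from the protocol is therefore not an error in itself.

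A further tempting reading, that Cohort 3 will look less safe, is true only in expectation, as the binomial results show. What the objections leave is that the protocol does fix numerator, denominator and grouping for a primary objective, and those displays cannot answer the rate question.

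**Conclusion.** The point holds as a limit on what the stated table can show. It is not a demonstration of a biased analysis. The crude percentage by cohort describes whole-regimen risk correctly. It cannot by itself show whether longer dosing changes the event rate, because at an identical rate Cohort 3 is expected to read higher: about 43% against 30% in the worked example, with a largest gap of about 16 points over the risks examined. The durations are the protocol's own. The size rests on an assumed constant hazard and assumed risks. At 4 to 8 subjects per cohort the expected gap is at most about one subject, so it may not appear in the data at all. The change is worth making because it is nearly free and concerns a primary objective.

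**What to change.** Keep the crude table in section 11.4.3.1 and label it as risk over the whole regimen and its follow-up. Add there, or by cross-reference to the SAP if it already has them, events and first events per subject-time by cohort, separately for the treatment period and the common 84-day post-treatment period. State where the boundary between the periods falls, and that any cross-cohort remark about event rates uses these displays. Do not rest conclusions on a Day 0 to 112 cut. Word the rule so that it also covers Cohort 4, whose duration is open.

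Onset and end dates of events are already recorded (section 10.2.1), so no new data are needed. The cost is a sentence or two of text and one or two tables. The rates will be imprecise: four Cohort 2 subjects contribute only 4 × 28 = 112 subject-days of treatment time, against 4 × 91 = 364 in Cohort 3. The tables should therefore show events and subject-time as well as the rates.

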### **7.4 Vital Sign Measurements**

Vital sign assessments will include measurements of sitting blood pressure (mm Hg), heart rate (beats per minute), respiration rate (breaths per minute), pulse oximetry, and oral temperature (Celsius). Abnormal results are to be repeated after 5 minutes of rest. See [Table 6](#) for timing window allowances with respect to measurement collection.

Vital sign measurements will be collected after the subject has been sitting for 5 minutes. Subjects should be seated quietly for at least 5 minutes in a chair with their backs supported, their feet flat on the floor (legs uncrossed), and their arms bared on a hard surface, with the arm slightly abducted and bent, with palm up and the midpoint of upper arm at heart level. Correct cuff and bladder size should be utilized and the same cuff and arm should be used per subject throughout study.

Vital sign measurements are to be obtained immediately prior to the infusion; 15, 30, and 45 minutes after the start of the infusion; at completion of the infusion; 30 minutes, 1 hour, and 2 hours following completion of the infusion. Abnormalities in vital sign measurements will be graded in severity per the National Cancer Institute Common Terminology Criteria for Adverse Events (NCI CTCAE) scale Version 4.03.

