**8.3.2 Cohort 2: Treatment Days 14 and 28; Cohort 3: Treatment Days 42 and 91**

For Cohort 2 Days 14 and 28 ( $\pm 1$  day) and Cohort 3 Days 42 and 91 ( $\pm 1$  day), subjects will return to the clinic and the following procedures are to be performed prior to study drug infusion:

- Complete physical exam
- Vital sign measurements (sitting blood pressure, heart rate, respiratory rate, oral temperature) and pulse oximetry; to be measured immediately prior to the infusion
- Clinical safety laboratory tests (hematology, serum chemistry panel, urinalysis)
- Pregnancy test (*Cohort 3, Days 42 and 91 only*)
- PDAI
- PK sample collection (collected just prior to the start of the study drug infusion) (*Cohort 2, Day 28 only; Cohort 3, Day 91 only*)
- Immunogenicity sample collection (collected just prior to the start of study drug infusion)
- PD sample collection (collected just prior to the start of the study drug infusion)

- IgG, IgG subtypes (IgG1-4), IgA, IgM
- CIC
- Anti-Dsg (1 and 3) antibody titers
- Exploratory pemphigus immune response biomarkers
- Photography (*Cohort 3, Day 42 only*)

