#### **10.3.2 Management of Allergic or Infusion-Related Reactions**

As observed with all mAbs administered by IV infusion, infusion reactions to SYNT001 are possible. In general, infusion reactions to mAbs observed in human studies typically develop

[figure not shown]
within 30 minutes to 2 hours after the initiation of drug infusion, although symptoms may be delayed for up to 24 hours. These infusion reactions can occur with the first dose of a mAb and are generally mild in severity, although severe and even fatal reactions can occur.

Allergic and/or infusion-related reactions include hypersensitivity reactions and cytokine release syndromes. These reactions are experienced by subjects during or within hours of the infusion of mAb therapy. Symptoms can include flushing, alterations in heart rate and blood pressure, dyspnea, bronchospasm, back pain, fever, urticaria, edema, nausea, and all types of rashes. Anaphylaxis is recognized as a severe, life-threatening, generalized, or systemic reaction. This is a medical emergency characterized by rapidly developing life-threatening airway and/or breathing and/or circulation problems usually associated with skin or mucosal changes.

Management of Grade 1 infusion reactions include interrupting the infusion or decreasing the rate of infusion by 50% and observing. Symptoms may also be treated as needed with medications such as diphenhydramine, hydrocortisone, or acetaminophen, either alone or in combination, depending on the subject's signs and symptoms. If the infusion is interrupted or the infusion rate is decreased, it is important to note that all study drug infusions must be completed within 4 hours of SYNT001 preparation.

[figure not shown]
Management of Grade 2 and higher infusion reactions should include stopping the infusion of study drug. Continued treatment with SYNT001 is prohibited following Grade 2 or higher infusion reactions. See [Figure 2](#) and [Figure 3](#) for details on the management of Grade 2 and Grade 3 infusion reactions. Allergic or infusion-related reactions will be graded in severity and managed based on NCI CTCAE Version 4.03 (see [Table 9](#)).

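### From dose 2 onward, the only planned change score for vital signs adds drift since Day 0 to the acute infusion change; a same-visit change score would separate the two at almost no cost

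*Protocol*

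**What the plan says.** Section 11.4.2 of the protocol fixes one reference for the whole study: "Baseline will be defined at the last value obtained prior to the first dose of study drug". Section 11.4.3.1 applies it to vital signs: "Vital sign measurements and change from baseline will be summarized at each scheduled time point by cohort using descriptive statistics". That sentence plans two summaries at every scheduled time point, the measured value and its change from baseline. The synopsis mentions only the measured values.

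The time points are set in section 7.4: "Vital sign measurements are to be obtained immediately prior to the infusion; 15, 30, and 45 minutes after the start of the infusion", and then "at completion of the infusion; 30 minutes, 1 hour, and 2 hours following completion of the infusion". The footnotes to Tables 2, 3 and 4 repeat this schedule, for vital signs and for pulse oximetry, on every dosing day. Each infusion therefore has one pre-infusion reading and seven later ones. Nowhere does the protocol define a change from the same visit's pre-infusion value.

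The synopsis gives the number of infusions: "Cohort 1: 10 mg/kg, 5 weekly IV doses", the same number for Cohort 2, and "14 weekly IV doses" for Cohort 3. Section 10.3.2 treats infusion reactions as possible and lists their signs: "Symptoms can include flushing, alterations in heart rate and blood pressure, dyspnea".

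**The concern.** Readings at 15, 30 and 45 minutes, at the end of the infusion and over the next 2 hours are taken to show what the infusion does. The natural reference is the reading taken just before that infusion. The protocol collects it at every dose but uses it as a reference only at dose 1, where it is also the study baseline.

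At later doses the planned change compares a reading during the infusion with one taken up to 13 weeks earlier. Ordinary visit-to-visit variation, change in disease, or treatment of co-existing conditions in between all enter the score. A rise since Day 0 can offset an acute fall, and a fall since Day 0 can look like an infusion effect at all seven time points. Vital signs are part of the primary safety endpoint, so these tables will be read for acute effects.

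**Working it through.** The plan gives no figure of its own to reproduce. The check has four steps.

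**1. What the planned score contains.** For infusion k, write pre_k for the same-visit pre-infusion value, post_k for any of the seven later readings and D0 for the baseline. Then

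post_k − D0 = (post_k − pre_k) + (pre_k − D0).

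The first term is the acute change and the second is drift. At dose 1, pre_1 is the Day 0 reading, so the drift term is zero. From dose 2 it need not be.

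**2. How many readings are affected.** The inputs are seven later readings per infusion (section 7.4), and 5 or 14 weekly infusions (synopsis), ending on Day 28 or Day 91 (Tables 2 to 4).

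| | Infusions after the first | Readings affected per subject | Age of reference |
|---|---|---|---|
| Cohorts 1 and 2 | 4 of 5 (80%) | 7 × 4 = 28 of 7 × 5 = 35 | 7 to 28 days |
| Cohort 3 | 13 of 14 (93%) | 7 × 13 = 91 of 7 × 14 = 98 | 7 to 91 days |

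**3. What the planned tables still show.** The pre-infusion reading is itself a scheduled time point, so it has its own row. Subtracting mean(pre_k) from mean(post_k) gives the mean acute change, provided the same subjects contribute to both rows. The distribution of individual changes does not follow from the two rows. Reassigning the post-infusion readings among subjects leaves every raw-row statistic unchanged but alters each subject's own change. With four subjects, one fall of 20 mmHg and three of zero give a mean of (−20 + 0 + 0 + 0)/4 = −5 mmHg, the same as four falls of 5. Only the minimum or a count of within-infusion changes tells these apart, and neither is planned.

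**4. Illustrative size.** All inputs here are assumptions; none is in the protocol. Take an acute effect with mean −10 mmHg and SD 5, measurement SD 4 on each reading, mean drift d of 0, 5 or 10 mmHg, and between-visit SD s of 5, 10 or 15 mmHg.

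- Change from Day 0 has mean −10 + d and SD √(4² + s² + 5² + 4²) = √(57 + s²). The mean is −10, −5 or 0, and the SD is about 9.0, 12.5 or 16.8. In simulation the share of subjects with a fall of 20 mmHg or more ran from 1% (d = 10, s = 5) to 28% (d = 0, s = 15).
- Change from the same-visit value has mean −10 and SD √(4² + 5² + 4²) = √57 ≈ 7.5, with about 9% falling by 20 mmHg or more, whatever the drift.
- The difference between the two mean rows was −10 in all nine scenarios, which confirms step 3.

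The gain in precision can also be written as SD of change = σ√(2(1 − ρ)). With assumed σ = 15 mmHg, ρ = 0.5 with Day 0 gives 15.0, and ρ = 0.8 with the same-visit value gives 9.5. The SE at n = 4 is then 7.5 against 4.7. The variance cut is 1 − (1 − 0.8)/(1 − 0.5) = 60%. For the pair 0.6 and 0.75 it is 37.5%, and for 0.4 and 0.85 it is 75%.

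**The case against.** The strongest answer is that the plan does not rest on the change score. Measured values are summarised at every time point, including the pre-infusion one. A reader might infer that an acute fall disappears from the output when pressure has risen since Day 0. The documents do not support that: the raw rows show the mean fall, and the pre-infusion change row shows the drift. This part of the objection stands. It leaves only the spread, the extremes and the counts.

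Second, infusion reactions are not found mainly through these tables. Abnormal readings are repeated and graded by CTCAE (section 7.4), reactions have their own grading and management (section 10.3.2, Table 9), adverse events are summarised by worst grade, and all data are listed. With 4 to 8 subjects per cohort, listings can be read subject by subject. This also stands, with one limit: in Appendix 1, hypotension and sinus tachycardia are graded by symptoms or need for intervention, not by the size of the change during an infusion.

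Third, section 11.4.1 lets the SAP, which is not at hand, add analyses. It may well do so. The point is limited to the reference that the protocol itself fixes for every time point.

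Fourth, the pre-infusion value is not a perfect bracket. Table 6 allows it up to 240 minutes before the infusion, and section 7.12 permits prophylactic medication. It is still far closer in time than Day 0.

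Two further inferences are tempting and should not be drawn. The protocol does not call infusion reactions the main expected acute harm. It calls them possible, names no events of special interest (section 10.4), and reports headache as the commonest event in the earlier study. Nor do the monkey data show that reactions come at later doses in general. Section 2.2 reports flushing and swelling after the third dose in one 5-week study and gives no dose number for the fatal reaction in the 14-week study. Section 10.3.2 says that reactions to antibodies can occur at the first dose, which this point does not touch.

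**Conclusion.** The point holds in a limited form. From dose 2 onward, the only planned change score for readings during and after an infusion mixes the acute change with drift since Day 0. That covers 28 of 35 such readings per subject in Cohorts 1 and 2 and 91 of 98 in Cohort 3. This follows from the protocol's own definitions and schedule and needs no assumption. What the tables lose is the SD, minimum, maximum and number of subjects with a large within-infusion change. The mean acute change is not lost, provided the same subjects contribute to both rows.

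The mmHg, SD and SE figures are illustrations that depend on assumed variances and correlations. As the safety analysis is purely descriptive, no test or threshold turns on them. A Day 0 baseline is not an error for longer-term change, and bedside management is unaffected. This is a modest improvement to the safety tables.

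**What to change.** In section 11.4.3.1, keep the raw values and the change from the pre-first-dose baseline, and add one sentence. Readings of vital signs and pulse oximetry from the start of each infusion to 2 hours after it will also be summarised as change from that visit's own pre-infusion value, by dose number and cohort, including the minimum and maximum. The new summary should stand beside the Day 0 change and not replace it, so that cumulative change at these time points stays visible.

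The cost is one derived variable and an extra set of table columns. All the readings are already collected, and no dose, visit or clinical rule changes.
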